1.2 Santalis Oral Mucositis Treatment

East Indian sandalwood is a tall evergreen tree native to southern India. The oil derived from this tree is composed almost exclusively of closely related sesquiterpenoids. The alcohols, alpha- and beta-santalol, are primarily responsible for the oil's odor and comprise approximately 70% of the oil. Both the wood (in powder form) and oil of the East Indian sandalwood tree have been used to treat a variety of skin and general health conditions. In traditional Indian (Ayurvedic) medicine, East Indian sandalwood oil (EISO) was used as a

treatment for inflammatory and eruptive skin diseases ^{2,3}. Traditional Chinese medicine also lists sandalwood as a treatment for gonorrhea ⁴, as well as for epigastric pain, chest pain, and vomiting⁵. In Europe, sandalwood has been used to treat fever and pain.

Sandalwood oil is a widely available item of commerce with minimal restrictions on the claims that vendors can make as to its potency, safety, and efficacy. Most sandalwood oils offered for sale are poorly characterized and may be of low grade and often contain residual solvents, adulterants, other essential oils, synthetic fragrances, and/or bulking or extending agents. Such materials are not generally manufactured and tested in accordance with the US FDA's 2004 Botanical Drug Development Guidelines and do not comply with the ISO specifications for EISO. There are a number of websites and documents that support the safe use of many essential oils, including sandalwood oil, on babies and children. It is not uncommon for consumers/parents to consult these sources, purchase sandalwood oil from any number of sources, and formulate their own treatments (sandalwood oil diluted in carrier oils), again with no regulation or controls for use on their children. Nevertheless, there have been very few reports of safety issues in the public domain.

Santalis plans to evaluate the safety and efficacy of their proprietary medical grade EISO, as the active ingredient in an oral mucositis treatment, in subjects with a high risk of developing oral mucositis during cancer therapy in a highly controlled environment consistent with prescription drug development guidelines. The initial observation of EISO as an efficacious preventive and therapeutic agent for oral mucositis came from a cancer patient who was undergoing chemotherapy (personal communications). It is Santalis' interest and belief that this observation may carry much further implications. As oral mucositis significantly affects patients' quality of life and therapeutic outcome, and there are few preventive and therapeutic agents with clinically proven efficacy available, a new treatment in managing radiation and chemotherapy induced oral mucositis, if proven efficacious, would benefit cancer patients tremendously.

The initial proposed clinical study will be conducted in adult head and neck cancer patients. This will be an open-labeled, proof of concept trial to evaluate the efficacy, safety and tolerability of EISO in a form of oral rinse as adjunctive therapy to standard of care. Santalis believes that the proposed study is a prudent and appropriate approach to investigate the potential of their product to prevent or improve oral mucositis symptoms commonly seen in patients undergoing radiotherapy with or without chemotherapy.

2. OBJECTIVES

The objectives of this trial are:

- To evaluate the efficacy of SAN005 when administered to adults for the prevention and treatment of radiation-induced oral mucositis

- To evaluate the safety of SAN005 when administered to adults for the prevention and treatment of radiation-induced oral mucositis
- To evaluate the tolerability of SAN005 when administered to adults for the prevention and treatment of radiation-induced oral mucositis

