3. STUDY PLAN

3.1 Overall Study Design

This trial will be a single-center, open-label, proof of concept trial to evaluate the efficacy, safety and tolerability of SAN005 treatment regimen when administered to adults at least 18 years of age for the prevention and treatment of oral mucositis.

Subjects will enter the Screening Period once the informed consent process has been completed. Subjects who are scheduled to receive radiation with or without concurrent chemotherapy and meet all of the inclusion criteria and none of the exclusion criteria will be eligible for the study:

Once subject eligibility is confirmed the subject will start SAN005 treatment on Day 1 of their radiation treatment. All subjects will receive active medication in the study with the first dose administered on Day 1.

Subjects will be instructed on the administration of study medication thrice daily till oral mucositis resolves. Subjects will return to the clinic once a week while receiving radiation and then once every two weeks once their radiation has been completed and then until their mucositis has resolved for the Final Study Visit.

Preliminary Efficacy Evaluation will be the severity of pain rated by the NRPS and mucositis grade by RTOG criteria at Visit 7 (Day 36). Additional secondary efficacy evaluations will include the severity of pain rated by the NRPS and mucositis grade by RTOG criteria at each study visit, frequency of the PEG tube for feeding during the duration of treatment and weight loss from baseline through Visit 5 and 7. The time of mucositis onset and duration will also be used in assessing efficacy. Additional secondary and exploratory endpoints will be outlined in the statistical analysis plan. The overall efficacy is determined by comparing the data to historical controls.

Safety will be assessed by evaluating adverse events (AEs) with respect to severity, duration, and relationship to study drug. In addition tolerability evaluations will be performed at each study visit.

During the active treatment period, subjects will return to the study site according to the study schedule for interim assessments, review of subject dosing diaries, and assessment of concomitant medication and adverse events (AEs).

The study design is summarized in Figure 3-1.

Figure 3-1 **Study Design**

Pretreatment	Treatment		Follow-up
Day 0	Day 1 Baseline	Day 8,15,22,29,36,43 (\pm 2 day, weekly)	Every other week until mucositis resolves or it reaches Visit 10

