3.2 Study Endpoints

Primary efficacy will be assessed by the numerical rating pain scale (NRPS) and RTOG mucositis grade at Visit 7 (Day 36).

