4.2 Inclusion Criteria

Patients will be included in the trial if they meet all of the following criteria:

1. Subjects with head and neck cancer involving the oropharynx or oral cavity, who are expected to undergo high dose radiation therapy (i.e., ≥ 60 Gy) that typically results in oral mucositis, with or without concurrent chemotherapy or biologic targeted therapy.
2. At least 18 years of age
3. Estimated survival of at least 6 months.
4. No prior radiation therapy to the head and neck area, and no chemotherapy within the last year except for induction chemotherapy delivered (or to be delivered) prior to the current course of radiation therapy
5. Female subjects of child-bearing potential must agree to use an adequate form of contraceptive (e.g., hormonal, barrier method or abstinence) prior to study entry and for the duration of the trial.
6. Are willing to refrain from using other treatments for oral mucositis until they consult with the study investigator(s).
7. Are able to give written informed consent in a manner approved by the Institutional Review Board and comply with the requirements of the study.

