4.3 Exclusion Criteria

Patients will be excluded from the trial if they meet any of the following criteria:

1. Have preexisting mucositis from other causes.
2. Are immunosuppressed or in chronic use of immunosuppressive drugs.
3. Have a known sensitivity to any of the constituents of the test product including sensitivities to sandalwood oil, fragrances or any member of the Compositae family of vascular plants (e.g., sunflowers, daisies, dahlias, etc.).
4. ECOG performance status ≥ 3
5. Unwilling or unable to follow the protocol requirements.
6. Have any condition that in the opinion of the investigator would confound the efficacy,

safety and tolerability assessments, such as oral thrush.

7. Have participated in any clinical trial in the previous 30 days.
8. Are pregnant, breastfeeding, or unwilling to practice an acceptable form of birth control during the study.

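### The objective claims efficacy in treatment as well as prevention, but every subject starts SAN005 before mucositis, and the duration measure has no value for subjects who never develop it

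*Combined protocol and SAP*

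**What the plan says.** The efficacy objective in Section 2, repeated in the synopsis, is "To evaluate the efficacy of SAN005 when administered to adults for the prevention and treatment of radiation-induced oral mucositis". The design statements in the synopsis and Section 3.1 pair prevention and treatment in the same way.

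On timing, Section 3.1 says: "Once subject eligibility is confirmed the subject will start SAN005 treatment on Day 1 of their radiation treatment", and "All subjects will receive active medication in the study with the first dose administered on Day 1". Sections 5.0 and 7.3.2 confirm that there is no randomization and that everyone receives active product.

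Two eligibility rules mean that subjects enter without mucositis. Section 4.3 excludes those who "Have preexisting mucositis from other causes", and Section 4.2 requires "No prior radiation therapy to the head and neck area".

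On duration, Section 3.1 says: "The time of mucositis onset and duration will also be used in assessing efficacy". On the comparator, the same section says: "The overall efficacy is determined by comparing the data to historical controls".

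The combined document does not define the grade that counts as onset, what counts as resolution, the value for a subject who never develops mucositis, or the handling of mucositis still present at Visit 10. Section 8.5.4 leaves the methods for secondary endpoints to the SAP.

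**The concern.** There are two linked problems.

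**The claim.** To show that a product treats mucositis, one needs subjects who start it once mucositis is present, or a comparison that isolates dosing after onset. This trial has neither. A subject whose mucositis heals quickly may have had a milder case because of earlier dosing, may have healed faster because of later dosing, or both. A treatment conclusion from these data would go beyond the design.

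**The duration measure.** In ordinary use, duration runs from onset to resolution, so it exists only in subjects who have an onset. On SAN005, who has an onset depends on whether the product prevented it. Historical patients who developed mucositis passed no such filter. Matching the historical series on baseline factors does not remove the difference, because it arises after the first dose. At stake is a secondary efficacy comparison that could mislead in either direction in a trial aiming for 10 completers.

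**Working it through.** **1. Is there any group from which a treatment effect could be isolated?**

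| Question | Document | Consequence |
|---|---|---|
| When does dosing start? | Day 1 of radiation, all subjects (Section 3.1) | No start after onset |
| Can mucositis be present then? | Mucositis from other causes and prior head and neck radiation are ruled out (Sections 4.3, 4.2) | Subjects start free of mucositis |
| Is there a concurrent or delayed-start group? | No (Sections 5.0, 7.3.2) | No internal contrast |
| Does dosing continue once mucositis appears? | Synopsis: for the duration of radiation. Section 3.1: until mucositis resolves. Table 7-1: about 10 weeks or until it resolves | Exposure after onset is likely but inconsistently specified, and always follows preventive dosing |

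No group isolates a treatment effect.

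**2. How far can developers-only duration mislead?** The documents give no incidence or duration figures. All inputs in this step are assumptions, and the results show only direction and rough size.

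*Hand example.* Suppose that, untreated, 30% of subjects have 14 days of mucositis and 70% have 40 days. The mean is 0.3×14 + 0.7×40 = 32.2 days. If the product prevents every 14-day case and changes nothing else:

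- the mean among developers is 40.0 days (40.0/32.2 = 1.24, 24% longer);
- the mean over all treated subjects is 0.7×40 = 28.0 days (28.0/32.2 = 0.87, 13% shorter).

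This is an extreme case, so a range is needed.

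*Range.* Assume a latent duration with mean 35 days and SD 14 days, correlated 0.6 with a susceptibility that decides onset. Vary untreated incidence from 60% to 95% and the share of cases prevented from 20% to 60%. For incidence p, the mean among developers is about 35 + 14×0.6×φ(z)/p, where z is the (1−p) normal quantile and φ the normal density. The worked cell has 90% incidence and 40% prevented, so incidence on product is 0.9×0.6 = 0.54.

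- Control: 35 + 8.4×0.1755/0.90 = 36.6 days (36.7 by simulation with a one-day floor).
- Model A, mildest cases prevented and the rest unchanged: 35 + 8.4×0.3969/0.54 = 41.2 days.
- Model B, severity lowered in everyone by 1.181 SD of susceptibility, which gives the same incidence: 41.2 − 8.4×1.181 = 31.3 days.

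Simulated means in days (2,000,000 draws):

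| Incidence, prevented | Developers: control | Developers: A | Developers: B | All subjects: control | All subjects: A | All subjects: B |
|---|---|---|---|---|---|---|
| 60%, 20% | 40.4 | 42.0 | 39.4 | 24.3 | 20.2 | 18.9 |
| 80%, 40% | 38.0 | 42.0 | 34.5 | 30.4 | 20.2 | 16.6 |
| 90%, 40% | 36.7 | 41.2 | 31.3 | 33.0 | 22.3 | 16.9 |
| 95%, 60% | 35.9 | 43.4 | 27.1 | 34.2 | 16.5 | 10.3 |

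Under Model A, developers look 1.6 to 7.5 days worse. With 10 subjects, the chance that their developers' mean exceeds a historical mean fixed at the control value is 0.61 to 0.87. Under Model B they look better in every cell. Counted over all subjects, with zero for those without mucositis, both models favour the product throughout. In the 90%, 40% cell under Model A, the chance of looking worse falls from 0.80 to 0.07.

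*When selection is slight.* With 95% incidence and 5% of cases prevented, incidence on product is 0.9025. Model A then gives 35 + 8.4×0.1723/0.9025 = 36.6 days against 35 + 8.4×0.1031/0.95 = 35.9, a gap of 0.7 days.

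**3. Does the end of observation matter?** If radiation ends near Day 43 (Visit 8), Visits 9 and 10 fall near Days 57 and 71. The longest observable duration is then 71 − 15 = 56 days for onset on Day 15 and 71 − 36 = 35 days for onset on Day 36. A product that only delays onset would appear to shorten duration, so this cap can flatter it.

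**The case against.** The strongest reply is that the protocol describes no developers-only analysis. It leaves duration undefined and passes secondary methods to the SAP, where a zero-day rule would remove the problem. This stands, so the point concerns a gap and its most natural reading, not a stated error.

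A reader might infer that duration is the only evidence on established mucositis. The documents do not support that. Section 3.1 lists NRPS and RTOG grade at each study visit as secondary evaluations, Section 6.2.3 continues both through follow-up, and NRPS is recorded daily between visits. These serial scores do not require an onset unless someone restricts them to developers.

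A reader might also infer that nobody is on product while they have mucositis. Section 3.1 and Table 7-1 say otherwise, and Section 6.2.3 provides for dispensing in follow-up. What remains true is that dosing after onset always follows dosing before it.

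Finally, the study is small, is expressly not powered, and describes its secondary endpoints without a decision rule. That limits the consequence, but it does not make a treatment claim supportable.

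**Conclusion.** The point holds in two parts. First, the design cannot support a separate conclusion on treatment of established mucositis. This follows from the documents alone. Second, duration compared with historical controls is open to selection bias if it is read as onset to resolution among developers. The size depends on assumptions: over the ranges tried, 1.6 to 7.5 days against the product if the mildest cases are prevented, no reversal if severity falls in everyone, and little bias if nearly all subjects develop mucositis.

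A reader might go further and infer that the design will make a working product look harmful. That is not supported: the direction depends on how the product acts, and the Visit 10 cap can push the other way. The primary measure, NRPS and RTOG grade at Visit 7 (Section 3.2), does not condition on onset and is not touched by this point. The change should be made, but the primary result does not depend on it.

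**What to change.** 1. In the synopsis, Section 2 and Section 3.1, state the efficacy objective as prevention or reduction of mucositis when SAN005 is started with radiation. Draw no separate treatment conclusion.
2. In Section 3.1 and the SAP, define duration as the number of days at or above a set RTOG grade (for example Grade ≥2 and Grade ≥3) over a fixed window from Day 1. Count all treated subjects, with zero days if the grade is never reached.
3. State how days between weekly and two-weekly visits are assigned, and how mucositis unresolved at Visit 10 is handled.
4. Derive the historical figure by the same definition and over the same window. If the historical data do not allow this, make no comparison on duration.
5. Report duration among developers as description only, with the number of subjects who contribute.
6. Reconcile the synopsis with Section 3.1 and Table 7-1 on how long dosing continues.

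The cost is a narrower claim and a little more analysis work. The visits and gradings already planned supply the trial's own data. The historical data may be harder to obtain in this form.

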3. STUDY PLAN

3.1 Overall Study Design

This trial will be a single-center, open-label, proof of concept trial to evaluate the efficacy, safety and tolerability of SAN005 treatment regimen when administered to adults at least 18 years of age for the prevention and treatment of oral mucositis.

Subjects will enter the Screening Period once the informed consent process has been completed. Subjects who are scheduled to receive radiation with or without concurrent chemotherapy and meet all of the inclusion criteria and none of the exclusion criteria will be eligible for the study:

Once subject eligibility is confirmed the subject will start SAN005 treatment on Day 1 of their radiation treatment. All subjects will receive active medication in the study with the first dose administered on Day 1.

Subjects will be instructed on the administration of study medication thrice daily till oral mucositis resolves. Subjects will return to the clinic once a week while receiving radiation and then once every two weeks once their radiation has been completed and then until their mucositis has resolved for the Final Study Visit.

Preliminary Efficacy Evaluation will be the severity of pain rated by the NRPS and mucositis grade by RTOG criteria at Visit 7 (Day 36). Additional secondary efficacy evaluations will include the severity of pain rated by the NRPS and mucositis grade by RTOG criteria at each study visit, frequency of the PEG tube for feeding during the duration of treatment and weight loss from baseline through Visit 5 and 7. The time of mucositis onset and duration will also be used in assessing efficacy. Additional secondary and exploratory endpoints will be outlined in the statistical analysis plan. The overall efficacy is determined by comparing the data to historical controls.

Safety will be assessed by evaluating adverse events (AEs) with respect to severity, duration, and relationship to study drug. In addition tolerability evaluations will be performed at each study visit.

During the active treatment period, subjects will return to the study site according to the study schedule for interim assessments, review of subject dosing diaries, and assessment of concomitant medication and adverse events (AEs).

The study design is summarized in Figure 3-1.

Figure 3-1 **Study Design**

Pretreatment	Treatment		Follow-up
Day 0	Day 1 Baseline	Day 8,15,22,29,36,43 (\pm 2 day, weekly)	Every other week until mucositis resolves or it reaches Visit 10
Visit 1	Visit 2	Visit 3 to 8	Visit 9 and 10

3.2 Study Endpoints

Primary efficacy will be assessed by the numerical rating pain scale (NRPS) and RTOG mucositis grade at Visit 7 (Day 36).

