- Request the subject to complete Day 1 of the diary and review for completeness and accuracy

Visit 3 to 8

Clinic visit with a radiation oncologist once a week till the end of treatment.

All study visits will have a \pm 2 day visit window during the radiotherapy.

- Query for adverse events
- Update concomitant medications and PEG tube usage
- Review the diary for the previous week
- Query for treatment regimen compliance
- Collect the study medication and weigh the study medication to determine usage
- Administer the QoL Questionnaire
- Administer the Numerical Rating Pain Scale (NRPS) as related to mouth pain and pain with swallowing. The NRPS will be recorded daily by the subjects between study visits
- Inspect the oral cavity and grade mucositis according to the RTOG Scale
- Record the subject's tolerability to the study drug
- Instruct the subject to return for the next study visit with study medication container and diary

Follow-up Period

Visit 9 to 10

Clinic visit with a radiation oncologist every other week after completion of radiotherapy until either mucositis resolves or it reaches Visit 10, whichever is earlier.

All study visits will have a \pm 2 day window during the follow-up period.

- Query for adverse events
- Update concomitant medications and PEG tube usage
- Review the diary for the previous week.
- Query for treatment regimen compliance
- Collect the study medication and weigh the study medication to determine usage
- Administer the QoL Questionnaire
- Administer the Numerical Rating Pain Scale (NRPS) as related to mouth pain and pain with swallowing. The NRPS will be recorded daily by the subjects between study visits.
- Inspect the oral cavity and grade mucositis according to the RTOG Scale
- Record the subject's tolerability to the study drug
- Instruct the subject to return for the next study visit with study medication container and diary

Trial Contacts

Name	Affiliation / Address	Responsibility
Santalis Corporation	[name] ☎ [contact] ✉ [contact]	Sponsor
[name].	Santalis Corporation [name] ☎ [contact] ✉ [contact] e-mail: [contact]	Sponsor Manager and contact for SAEs

Table of Contents

Contents

TITLE PAGE	1
Trial Contacts	6
Table of Contents.....	7
List of Tables.....	9
List of Figures	10
LIST OF ABBREVIATIONS AND DEFINITION OF TERMS	11
1 INTRODUCTION.....	12
1.1 Oral Mucositis	12
1.2 Santalis Oral Mucositis Treatment.....	12

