4. SELECTION OF STUDY POPULATION

4.1 Number of Subjects Required

An estimated number of 15 patients at least 18 years of age will be enrolled in this study to ensure 10 analyzable patients who complete the study. Dropouts secondary to poor compliance or patients who have more than two weeks of radiation treatment break will be excluded and will be replaced by enrolling more patients.

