7.3 Dosing Regimen

Subjects are to administer the treatment regimen according to the following schedule and order:

The following treatment products will be provided:

- Mouth Rinse— Take 30 ml by mouth each time. Swish for 30 seconds and spit. Use the rinse three times daily, including weekends when radiotherapy is not delivered, ideally 15 minutes after meals and refrain from eating or drinking for one hour after rinsing.

The investigational products contain ingredients commonly found in other oral products. The site staff will initially be responsible for teaching how to use SAN005, and then the subject will be instructed on the procedure for self- administration at home.

Subjects will be supplied with a patient dosing diary during the treatment period and will be instructed to answer several questions about their experience with the treatment regimen. The investigator or designee should collect and review the diary with the subject at every visit.

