7.6.1 Pain Assessment

At each Study Visit the NRPS will be recorded for mouth pain and pain upon swallowing. For the primary efficacy assessment the NRPS scale at baseline will be compared to Week 5. Subjects that complete at least 80% of treatments as determined by the diary and confirmed by the weight of the returned study product will be included in the efficacy analysis.

If possible, the same investigator who completes the scoring at Baseline should complete all subsequent assessments for the patient.

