8.5.4 Efficacy Analysis

The primary data analysis set for efficacy analyses will be the PP defined in Section 8.4.3. The primary analysis will be the determination of the severity and intensity of mucositis from Baseline to Visit 7 (Day 36).

The secondary efficacy endpoints analysis will be summarized using standard statistical methods and outlined in the Statistical Analysis Plan (SAP). In general, categorical endpoints will be tabulated by number, percentage, and a 95% 2-sided confidence interval (exact methodology) will be estimated. Continuous endpoints (i.e., percent change from baseline) may be summarized using descriptive statistics (N, mean, median, standard deviation, and range).

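### The primary efficacy reading stops at calendar Day 36, before radiotherapy is scheduled to end and at unequal doses, and no per-subject worst mucositis grade is defined

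*Combined protocol and SAP*

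**What the plan says.** Section 3.2 assesses primary efficacy by the pain score (NRPS) and "RTOG mucositis grade at Visit 7 (Day 36"). Section 7.6.1 gives the same time point for pain: "For the primary efficacy assessment the NRPS scale at baseline will be compared to Week 5". Section 8.1 also takes the pain score from baseline to Visit 7, and section 8.5.4 says: "The primary analysis will be the determination of the severity and intensity of mucositis from Baseline to Visit 7 (Day 36"). None of these ties the reading to cumulative radiation dose, to the end of radiotherapy or to the worst grade reached.

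Figure 3-1 in section 3.1 puts Visits 3 to 8 on "Day 8,15,22,29,36,43", so one weekly treatment visit follows the primary one. The synopsis describes those visits as: "Clinic visit with a radiation oncologist once a week till the end of treatment". Inclusion criterion 1 (section 4.2) requires a planned dose of at least 60 Gy. Fraction size and number of fractions per week are not given, but section 7.3 tells subjects to use the rinse on all days, "including weekends when radiotherapy is not delivered".

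On interruptions, section 4.1 says that "patients who have more than two weeks of radiation treatment break will be excluded". Shorter breaks have no rule, and the analysis sets in section 8.4 do not mention breaks.

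Section 3.1 makes RTOG grade and pain at each visit secondary, adds time of onset and duration, and bases overall efficacy on a comparison with historical controls.

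**The concern.** The objective is prevention and treatment of mucositis caused by a full course of radiotherapy. Section 1.1 links severity to radiation dose and fractionation, and says that mucositis often leads to unplanned treatment breaks. A reading fixed by the calendar therefore has two weaknesses.

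First, if it falls before the course ends, it cannot tell a subject whose mucositis was prevented from one whose mucositis was only delayed. Second, subjects with breaks are read on the same day at a lower dose, and the break may itself be a consequence of severe mucositis.

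About 10 analysable subjects are expected (section 4.1), so each subject is worth 1/10, or 10 percentage points, in any proportion. One or two subjects whose Day 36 grade does not represent their course would move the result by 10 to 20 points.

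**Working it through.** **1. The plan's own visit days.** Day = 1 + 7 × (visit − 2). Visit 7 = 1 + 7 × 5 = Day 36 and Visit 8 = 1 + 7 × 6 = Day 43, as stated.

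**2. When radiotherapy is scheduled to end.** If Visit 8 is the last treatment visit, two-weekly follow-up gives Visit 9 on Day 43 + 14 = 57 and Visit 10 on Day 43 + 28 = 71. These are the first days of weeks 9 and 11, which matches the 9 to 11 weeks in section 6.1. The plan's timeline thus puts the end of radiotherapy at about Day 43, one week after the primary reading.

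**3. Dose by Day 36.** Assumptions: one fraction per weekday and 1.8 to 2.2 Gy per fraction. The first is suggested by section 7.3; the second is not in the documents. Days 1 to 35 hold 25 weekdays, and Day 36 falls on the same weekday as Day 1, so 26 fractions have been given whatever the starting weekday. Over the ±2 day window the count runs from 24 to 28.

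| Gy per fraction | Day 36 (26 fractions) | Window (24 to 28 fractions) | Day 36 after 10 missed fractions (16) |
|---|---|---|---|
| 1.8 | 46.8 Gy | 43.2 to 50.4 Gy | 28.8 Gy |
| 2.0 | 52.0 Gy | 48.0 to 56.0 Gy | 32.0 Gy |
| 2.2 | 57.2 Gy | 52.8 to 61.6 Gy | 35.2 Gy |

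On Day 36 itself every value is below 60 Gy. Only the late edge of the window at the largest fraction size passes it.

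**4. Effect of a permitted break.** Two weeks is 10 weekday fractions, so 26 − 10 = 16. At 2 Gy, two subjects both read on Day 36 can differ by 52 − 32 = 20 Gy. This is the extreme case, in which the longest permitted break falls entirely before Day 36. A later break does not change the dose at Visit 7.

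**5. When 60 Gy is reached.** Fractions needed: 60/1.8 = 33.3, so 34; 60/2.0 = 30; 60/2.2 = 27.3, so 28. On a weekday calendar these fall on Days 46 to 48, 40 to 42 and 38 to 40, depending on the starting weekday. Ten missed fractions add 14 days: Days 52 to 62 overall.

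**6. Sensitivity to the schedule.** At an assumed six fractions a week, 31 fractions are given by Day 36: 55.8 Gy at 1.8 Gy and 62.0 Gy at 2.0 Gy. With no weekend radiotherapy, that would need two fractions on one weekday, which the documents neither describe nor rule out.

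**7. Whether visit-by-visit tables give the worst grade.** They do not. If p7 and p8 are the proportions at grade 3 or worse at Visits 7 and 8, the proportion at that grade at either visit lies anywhere between max(p7, p8) and min(1, p7 + p8). The maximum has to be taken within each subject first.

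**The case against.** The case on the other side is substantial.

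- **No success rule.** A reader might infer that a subject with a mild grade on Day 36 and severe mucositis later would count as a success. The plan has no responder definition or threshold, and section 8.2 says that the study is not powered. The later event is outside the primary endpoint, but nothing classifies the subject as a success.
- **Direction of bias.** A reader might also infer that the early reading flatters SAN005. That depends on the historical controls. If they were graded around Week 5 under similar treatment, later mucositis is missed on both sides. If they supply worst grades, a Day 36 rate would compare favourably for that reason alone. The plan does not say which applies, so neither direction is shown.
- **Later data are not lost.** Grading continues to Visit 10 unless mucositis resolves first, and onset and duration are already named as efficacy measures. Severe mucositis before a break or after Day 36 can be recorded at those visits.
- **Breaks are partly handled.** Section 4.1 removes subjects with breaks of more than two weeks.
- **The dose figures rest on assumed fractionation.** This stands. The scheduled treatment visit on Day 43 does not depend on it.
- **Wording of section 8.5.4.** It can be read as covering the period up to Visit 7. Even so, the period ends on Day 36.
- **A worst-grade summary may exist elsewhere.** Sections 3.1 and 8.5.4 leave further endpoints to a statistical analysis plan, and no separate plan is among the documents supplied.

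These points limit the concern to what the primary endpoint covers and how evenly it covers it. They do not remove it.

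**Conclusion.** The point holds in a limited form. The primary reading precedes the scheduled end of radiotherapy by about a week. With one fraction per weekday of 1.8 to 2.2 Gy, it comes after about 47 to 57 Gy of a planned minimum of 60 Gy (43 to 62 Gy over the window). With the longest permitted break falling early, it could come at about 32 Gy at 2 Gy per fraction. The primary endpoint therefore cannot separate prevention from delay, and it mixes subjects at unequal doses.

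The effect on the trial's conclusion cannot be sized. The documents give no rate of mucositis arising after Day 36 and no description of how the historical controls were graded. It would go too far to say that the result is biased towards SAN005. For a small, descriptive proof-of-concept study, this is a worthwhile, inexpensive improvement to the analysis and not a defect that invalidates it.

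**What to change.** Keep the Day 36 reading as it stands and pre-specify the following beside it:

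1. Each subject's worst RTOG grade over Visits 3 to 10, and the proportion reaching grade 3 or worse with an exact two-sided 95% confidence interval. Section 8.5.4 already names that interval for categorical endpoints.
2. Each subject's worst NRPS score over the same visits, since pain is part of the primary assessment.
3. A rule that each summary is compared only with historical values of the same type: worst grade with worst grade, Week 5 with Week 5.
4. A listing of cumulative radiation dose at Visit 7 next to the Day 36 grade, so that subjects with breaks can be seen.

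The cost is one or two derived variables and one table, from grades and scores already collected, plus the dose listing. The protocol text does not list cumulative dose among the data collected. If it is not on the case report form, it has to be transcribed from the radiation record for up to 15 subjects. No visit, treatment or eligibility rule changes.
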